Appendix D. Modified Response Assessment In Neuro-Oncology (RANO)

The RANO criteria are extensions to the Macdonald criteria that incorporate T2/ FLAIR images to better capture lesion response (Wen et al, 2010). Here, the RANO criteria are further modified to capture pseudoprogression and delayed responses which may be observed in response to immunotherapies (Okada et al, 2015).

Patients require at least 1 bi-dimensionally measurable contrast-enhancing lesion that can be accurately assessed at baseline by magnetic resonance imaging (MRI) to be included in this a study.

Definitions:

- Measurable lesions contrast-enhancing lesions that can accurately be measured bidimensionally with $\geq 10\text{mm}$ longest diameter and $\geq 10\text{mm}$ perpendicular diameter and noted on more than one imaging slice.
- Non-measurable lesions – all other lesions, including small lesions, ie, bone lesions, leptomeningeal disease and cystic lesions that are not confirmed and followed by imaging techniques.

Documentation of index and non-index lesions:

- Index Lesions
 - All measureable lesions (up to 5) should be identified as index lesions, measured and recorded during screening.
 - Enhancing lesions should be selected based on size (largest cross-sectional area) and suitability for accurate repeat measure (clearly defined borders)
 - The sum of bidimensional products (total cross-sectional area of measurable lesions) for all enhancing measurable lesions at screening will be calculated and reported as the baseline disease burden.
 - Baseline disease burden will be the reference used to characterize radiographic objective tumor response.
 - Baseline or nadir, whichever is smaller, is used to calculate PD.
- Non-Index Lesions
 - All other lesions (or sites of disease) should be identified and recorded as non-index lesions during screening.
 - Measurable lesions located in previously irradiated sites that have not since shown documented progression are non-index lesions.
 - Incidental new lesions will be recorded and tracked as non-index lesions.
 - Measurement of non-index lesions is not required, but absence or presence and qualitative changes (unequivocal response, stable, unequivocal progression) should be recorded throughout the study.

Approved

Table 21. Measurement Summary

| Imaging modality | MRI |
|-----------------------------|--|

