If a subject has no tumor evaluation in the study, progression-free survival time will be censored at the date of the first administration of AMG 596.

Subjects who withdraw consent to participate in the study prior to disease progression will be censored at their last evaluable radiological assessment date.

Response Criteria (per modified RANO):

Complete Response (CR):

- Disappearance of all enhancing disease
- No new lesions
- Stable or improved T2/FLAIR
- No more than physiological steroids
- Clinically stable or improved
- Disappearance confirmed with follow-up scan after ≥ 4 weeks

Partial Response (PR):

- $\geq 50\%$ decrease in the sum of perpendicular diameters of enhancing disease from baseline
- Stable or improved T2/FLAIR
- Stable or decreased steroid dose
- Clinically stable or improved
- Decrease confirmed with follow-up scan after ≥ 4 weeks

Stable Disease (SD):

- Changes do not qualify for CR, PR or PD
- Stable or improved T2/FLAIR
- Stable or decreased steroid dose
- Clinically stable or improved

Progressive Disease (PD):

Any of the below

- $\geq 25\%$ increase in the sum of perpendicular diameters of enhancing disease from the lesser of baseline or nadir
- Or substantially worsened T2/FLAIR
- Or unequivocal progression in new lesions
- Or substantial clinical decline
- Increase confirmed with follow-up scan ≥ 4 weeks after initial observation.

Screening Date:

Screening date is defined as the date the informed consent was signed.

Study Day 1:

Day 1 is defined as the first day that investigational product is administered to the subject. The day before Day 1 is referenced as Day-1.

Study Day:

Post day of dose: study day = (study date - date of Study Day 1) + 1

Pre day of dose: study day = (study date – date of Study Day 1)

Time to Response:

Time to response is calculated as the number of days from the date of first administration of AMG 596 to the date of confirmation of first objective response per MRI scan (date of confirmation of first objective response – date of first dose of AMG 596+1).

If a subject did not respond, time to response will be censored at the date of the last evaluable response assessment.

If a subject has no tumor evaluation related to response assessment as per modified RANO criteria, time to response will be censored at the date of the first administration of AMG 596.

Time to Progression:

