Appendix D. Modified Response Assessment In Neuro-Oncology (RANO)

The RANO criteria are extensions to the Macdonald criteria that incorporate T2/ FLAIR images to better capture lesion response. Here, the RANO criteria are further modified to capture pseudoprogression and delayed responses which may be observed in response to immunotherapies ([Okada et al, 2015](#)).

Patients require at least 1 bi-dimensionally measurable contrast-enhancing lesion that can be accurately assessed at baseline by magnetic resonance imaging (MRI) to be included in this a study.

Definitions:

- Measurable lesions contrast-enhancing lesions that can accurately be measured bidimensionally with ≥ 10 mm longest diameter and ≥ 10 mm perpendicular diameter and noted on more than one imaging slice.
- Non-measurable lesions – all other lesions, including small lesions, ie, bone lesions, leptomeningeal disease and cystic lesions that are not confirmed and followed by imaging techniques.

Documentation of index and non-index lesions:

- Index Lesions
 - All measureable lesions (up to 5) should be identified as index lesions, measured and recorded during screening.
 - Enhancing lesions should be selected based on size (largest cross sectional area) and suitability for accurate repeat measure (clearly defined borders)
 - The sum of bidimensional products (total cross-sectional area of measurable lesions) for all enhancing measurable lesions at screening will be calculated and reported as the baseline disease burden.
 - Baseline disease burden will be the reference used to characterize radiographic objective tumor response.
 - Baseline or nadir, whichever is smaller, is used to calculate PD.
- Non-Index Lesions
 - All other lesions (or sites of disease) should be identified and recorded as non-index lesions during screening.
 - Measurable lesions located in previously irradiated sites that have not since shown documented progression are non-index lesions.
 - Incidental new lesions will be recorded and tracked as non-index lesions.
 - Measurement of non-index lesions is not required, but absence or presence and qualitative changes (unequivocal response, stable, unequivocal progression) should be recorded throughout the study.

Table of Measurement Summary

Imaging modality	MRI

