Sequences for this protocol	
 - Axial Pre Contrast (2D) T1 - Axial T2/FLAIR - Axial T2 - Axial Post Contrast (2D) T1 - Axial DWI (at selected sites) - Sagittal Post Contrast (3D) T1 (at selected sites)
Measurement technique	Bidimensional; sum of products of perpendicular diameters
Imaging intervals	Screening, every 10-12 weeks, SFUP, LTFU
Measurable lesions	Contrast-enhancing lesions with ≥ 10 mm longest diameter and ≥ 10 mm perpendicular diameter
Measurable disease	One to five index lesions

Table of Response Assessment

All % changes are calculated as change from baseline burden, except PD which is baseline or nadir.	
Complete response (CR)	
 • Disappearance of all enhancing disease • no new lesions • stable or improved T2/FLAIR • no more than physiological steroids • clinically stable or improved • Disappearance confirmed with follow-up scan after ≥ 4 weeks
Partial response (PR)	
 • $\geq 50\%$ decrease in the sum of perpendicular diameters of enhancing disease from baseline • stable or improved T2/FLAIR • stable or decreased steroid dose • clinically stable or improved • Decrease confirmed with follow-up scan after ≥ 4 weeks
Stable disease (SD)	
 • Changes do not qualify for CR, PR or PD • stable or improved T2/FLAIR • stable or decreased steroid dose • clinically stable or improved
Progressive disease (PD)	
 • Any of the below • $\geq 25\%$ increase in the sum of perpendicular diameters of enhancing disease from the lesser of baseline or nadir • or substantially worsened T2/FLAIR • or unequivocal progression in new lesions • or substantial clinical decline • Increase confirmed with follow-up scan ≥ 4 weeks after initial observation.

Responses (CR and PR) are dated at time of confirmation scan.

Progression (PD) is backdated to initial observation, if confirmed.

Patients with a neurological decline attributable to their underlying tumor requiring discontinuation of treatment without objective evidence of measurable radiographic disease progression at that time should be classified as having “clinical deterioration.” Every effort should be made to document the radiographic progression even after discontinuation of treatment.

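### The partial-response and progression thresholds are written on a sum of lengths, while the plan measures tumour burden as a sum of areas

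*SAP*

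**What the plan says.** SAP Section 5, Response Criteria (per modified RANO), sets two numerical thresholds:

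- PR: at least a 50% "decrease in the sum of perpendicular diameters of enhancing disease from baseline".
- PD, measurement-based criterion: at least a 25% "increase in the sum of perpendicular diameters of enhancing disease from the lesser of baseline or nadir".

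The PR and PD lines of the response table in SAP Appendix D and of protocol Table 22 carry the same wording.

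The rest of each Appendix D works with a different quantity. Baseline disease burden is an area: "The sum of bidimensional products (total cross-sectional area of measurable lesions) for all enhancing measurable lesions at screening will be calculated" (protocol; the SAP has the same sentence). The measurement summary in each document gives the technique as "Bidimensional; sum of products of perpendicular diameters". The index-lesion instructions add: "Baseline disease burden will be the reference used to characterize radiographic objective tumor response". The header of each response table reads: "All % changes are calculated as change from baseline burden, except PD which is baseline or nadir".

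**The concern.** A sum of perpendicular diameters is a length in mm. A sum of products of those diameters is an area in mm². A 50% or 25% change in one is not the same change in the other, so the criteria lines contradict the burden definition, the technique row and, for PR, the header directly above them. SAP Section 5 is the more exposed place: it repeats the criteria lines without the header, the burden definition or a reference to Appendix D.

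Objective response is CR or PR, so the PR line feeds ORR, time to response and duration of response. It also feeds the Group 2 futility guideline, which turns on single responders (0 of 10, 1 or fewer of 19, 2 or fewer of 26, 3 or fewer of 31). The PD line feeds TTP, PFS and the end of response. Protocol Section 7.9.2 says only that imaging may go to a central laboratory, and Section 3.2 plans about 12 or more sites, so consistent classification depends on the written rule.

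**Working it through.** **Plan's own figures.** The plan states no number for this point. The Group 2 ORR design that uses the response definition was recomputed exactly from the four futility bounds. Type I error is 0.0497 (stated 0.05) and power is 0.803 (stated 0.8). The probability of stopping at 10 subjects when ORR is 5% is 0.95^10 = 0.599 (stated 60%). The expected number of additional subjects is 15.55 − 6 = 9.55 (stated 9.6). These reproduce and do not depend on the wording. What is open is which scans count as responses.

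**Inputs.** The 50% and 25% thresholds come from SAP Section 5, the SAP Appendix D response table and protocol Table 22. Both Appendix Ds give the area measure and set the limits of up to five index lesions, each at least 10 × 10 mm.

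**Proportional change.** Let every diameter be multiplied by f (an assumption). The sum of diameters is then multiplied by f and the sum of products by f².

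- Length rule for PR: f = 0.5, so area changes by 0.5² − 1 = −75%.
- Length rule for PD: f = 1.25, so area changes by 1.25² − 1 = +56.25%.
- Area rule for PR: f = √0.5 = 0.707, so diameters change by −29%.
- Area rule for PD: f = √1.25 = 1.118, so diameters change by +12%.

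Under this assumption the readings disagree on PR for area falls from 50% to just under 75%, and on PD for area rises from 25% to just under 56.25%.

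**Examples.** These test the size threshold only; the other PR and PD conditions are set aside.

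| Case | Sum of diameters | Sum of products | By length | By area |
|---|---|---|---|---|
| 30×30 mm to 20×20 mm | 60 to 40 mm (−33%) | 900 to 400 mm² (−56%) | not PR | PR |
| 30×30 mm to 35×35 mm | 60 to 70 mm (+17%) | 900 to 1225 mm² (+36%) | not PD | PD |
| 50×50 mm and four 10×10 mm; the small ones vanish, the large one becomes 45×45 mm | 180 to 90 mm (−50%) | 2900 to 2025 mm² (−30%) | PR | not PR |
| 50×50 mm and four 10×10 mm; the small ones grow to 15.7×15.7 mm | 180 to 225.6 mm (+25.3%) | 2900 to 3486 mm² (+20.2%) | PD | not PD |

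The first two rows show the length rule calling PR and PD later than the area rule. The last two show it calling them earlier when lesions are unequal, because the sum of lengths gives small lesions more weight. The literal rule is therefore not simply conservative.

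**The case against.** The strongest reply is that the documents largely settle the matter. Each Appendix D defines burden as an area, makes that burden the reference for response, names the products as the technique and takes percentage changes from burden. Nobody is told to calculate a baseline sum of lengths. On this view a phrase was dropped and copied to three places, and an experienced assessor would use area. The heading of the criteria in SAP Section 5 names modified RANO, which has one home in each document, and the text assessors would use is probably protocol Table 22.

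Much of this stands: it shows which reading is intended. It does not remove the contradiction. The criteria lines under the header still name another quantity. For PD the header says only baseline or nadir, so the area reading there rests on the burden definition and the technique row. SAP Section 5 has none of these supports.

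Three limits on the impact also stand. PD can be met through T2/FLAIR worsening or new lesions, and death is a PFS event, so the effect on TTP and PFS is partial. The PD criteria also list clinical decline, and the protocol synopsis dates PD from clinical or radiographic progression, but the SAP counts only radiographic progression for TTP and PFS, so clinical decline alone does not bypass the measurement rule in those analyses. Group 2 admits non-measurable disease, where no size threshold applies. The futility rule is a guideline, not a binding stop.

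**Conclusion.** The concern holds. The PR and PD lines in SAP Section 5, SAP Appendix D and protocol Table 22 are wrong as written against the plan's own measure. Under proportional change the literal rule moves the PR threshold from a 50% to a 75% fall in area and the PD threshold from a 25% to a 56% rise. With several unequal lesions the error can run the other way. CR is unaffected because it does not use this measure.

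The lesion examples are illustrative. How many subjects would change category, and hence the effect on ORR, PFS or a futility decision, cannot be derived from the documents. The point should be fixed: it is a response definition behind the efficacy endpoints, and one reclassified responder can move a Group 2 cohort across a futility bound.

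**What to change.** In the PR and PD lines of SAP Section 5, the SAP Appendix D response table and protocol Table 22, insert *products of* before *perpendicular diameters*, so that the criteria match the plan's stated technique and burden definition. In SAP Section 5, add the basis for percentage change (baseline burden; for PD, the lesser of baseline or nadir burden) or a reference to Appendix D.

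The cost is one phrase in two lines at three places, plus one sentence. No extra data are needed because the products are already part of the planned measurement. The change to Table 22 is a protocol amendment and needs IRB/IEC approval under protocol Section 12.1, so it is sensibly made with the next amendment. The SAP can be corrected directly.

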The AMG 596 start dose based on preclinical evaluations for the estimation of the MABEL is [REDACTED] µg/day. Further pre-specified nominal AMG 596 doses for potential use in any dose escalation Arm are [REDACTED] µg/day. The dose level review team (DLRT) may consider treating at intermediate doses if required. If the MTD or a biological active dose considered the RP2D is not reached within the pre-planned nominal dose range, the DLRT may decide to expand the nominal dose range to dose levels [REDACTED] µg/day after careful consideration of all available safety, laboratory, and PK information. The preliminary estimate of the RP2D/MTD of AMG 596 will be done initially in subjects with recurrent disease (Group 1) and separately in subjects with maintenance treatment after SoC in newly diagnosed disease (Group 2) and separately for AMG 596 monotherapy and in combination with AMG 404. If the same AMG 596 doses are to be explored in monotherapy and in combination, the monotherapy cohort must be completed before enrollment in the combination cohort. In the multiple subject cohorts, a safety observation window of at least 72 hours must apply between start of subjects 1, 2 and 3 of each dose escalation cohort. Intra-subject dose escalation will be allowed to higher AMG 596 dose levels in subsequent treatment cycles

Approved

once a higher dose has been deemed safe by the DLRT. Subjects who do not proceed to a higher dose may continue at the original dose.

Group 1, Recurrent Disease

- *Dose Escalation in single subject cohorts*
 - AMG 596 monotherapy: In first cohorts AMG 596 will be administered as a cIV infusion for [REDACTED] at escalating doses with N=1 per cohort. In the single subject cohorts, only a limited number of subjects will be enrolled at dose levels anticipated to be lower than those at which visible pharmacodynamics activity including adverse events related to AMG 596 therapy will be expected. In addition, the investigator together with the subject will decide on subsequent treatment duration carefully. Subjects are allowed to stay on study in [REDACTED] cycles until discontinuation criteria apply.
 - Combination of AMG 596 with AMG 404: The starting dose of AMG 596 is [REDACTED] µg/day administered in [REDACTED] cycles and the defined AMG 404 dose is [REDACTED] mg every 4 weeks.
 - The cohort size will be increased to N=2-4 subjects (= Start of multiple subject cohorts) after observation of

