Subjects who withdraw consent to participate in the study prior to achieving objective response will be censored at their last evaluable radiological assessment date.

End of study:

Primary Completion:

The primary completion of study will occur when the last subject is assessed or receives an intervention for the purposes of final collection of data for the primary analysis. (The primary analysis will occur when target enrollment in Part 1 and Part 2 is complete and each subject either completes 6 months on study or withdraws from the study.)

End of Study:

The time when the last subject is assessed or receives an intervention for evaluation in the study. (The final analysis will occur at this time.)

Enrollment:

A subject is considered enrolled after meeting all eligibility criteria and treatment and cohort have been assigned for the study.

See protocol section 5.0 for further details.

Investigational Product:

The term investigational product is used in reference to AMG 596.

Maximum Tolerated Dose (MTD):

The MTD is defined as the maximum dose with the highest probability of the target toxicity probability interval (TPI), but with a less than 0.25 probability of an excessive or unacceptable TPI.

The target TPI is (0.20, 0.33] and TPIs of (0.33, 0.60] and (0.60, 1.00] are defined as excessive and unacceptable, respectively.

Overall Survival (OS):

The number of days from the date of first administration of AMG 596 to the date of death, regardless of cause.

Subjects who withdraw from treatment without withdrawing consent will be followed for survival status whenever possible. Subjects who are alive (no record of death) and are lost to follow-up will be censored at the date of last contact.

Objective Response (OR):

Tumor response assessment of either complete response or partial response (CR or PR) per modified RANO criteria.

Progression Free Survival (PFS):

The number of days from the date of first administration of AMG 596 to the date of radiological evidence of disease progression (date of MRI scan) or death, regardless of cause.

The following censoring strategies for missing assessment dates will be used for the progression free survival analysis:

If a subject's disease has not progressed and the subject is alive, progression-free survival time will be censored at the last date they are known to be progression-free (ie, the last evaluable radiological assessment date).

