Time to progression is calculated as the number of days from the date of first administration of AMG 596 to the initial date of radiographic progressive disease (PD) per MRI scan (Initial date of first PD – date of first dose of AMG 596+1).

The following censoring strategies for missing assessment dates will be used for the time to progression:

If a subject's disease has not progressed , time to progression will be censored at the last date they are known to be progression-free (ie, the last evaluable radiological assessment date).

If a subject has no tumor evaluation in the study, time to progression will be censored at the date of the first administration of AMG 596.

Subjects who withdraw consent to participate in the study prior to disease progression will be censored at their last evaluable radiological assessment date.

6. Analysis Sets

For all analyses, subjects will be analyzed according to the dose and treatment they received, not the dose and treatment to which they were assigned.

Safety Analysis Set

The analysis of all endpoints, unless noted otherwise, will be conducted on the Safety Analysis Set defined as all subjects that are enrolled and receive at least one administration of AMG 596.

DLT Evaluable Analysis Set

The DLT Evaluable Analysis Set will be used to summarize incidence of dose limiting toxicity (DLT). Subjects are classified as DLT-evaluable if they have had the opportunity to complete the DLT period and:

- Subject in the [REDACTED] cycle receiving a complete first cycle with 100% of the planned doses of investigational product, or
- Subject in the [REDACTED] cycle receiving at least 90% of the planned doses of investigational product or
- Subject that has experienced a DLT

Pharmacokinetic Analysis Set

The pharmacokinetic (PK) analysis set will contain all subjects for whom at least one PK parameter or endpoint can be adequately estimated.

Efficacy Analysis Set

All subjects that are enrolled and receive at least one administration of AMG 596 at the MTD will be included in the analysis of the secondary efficacy endpoints.

RANO Evaluable Analysis Set

All subjects that are enrolled and receive at least one administration of AMG 596 and who have at least one measurable lesion at baseline will be part of this analysis set.

7. Planned Analyses

There are 3 analyses (interim, primary and final) which are planned in the study.

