9.5 Efficacy Analyses

Unless otherwise specified, all subjects that are enrolled and receive at least one administration of AMG 596 at the MTD (the efficacy analysis set) will be included in the analysis of the secondary efficacy endpoints.

The following methods will be used with Kaplan-Meier analyses of efficacy endpoints.

- Estimation of the median and CI will use the Brookmeyer and Crowley (1982) method
- Landmark estimates (eg, 6 month PFS) will be estimated using the Kaplan-Meier curve and CI using Greenwood's formula to estimate the standard error (see [Kalbfleisch J.D. and Prentice R.L. \(1980\)](#))

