9.5.1 Analyses of Efficacy Endpoint(s)

Duration of Response:

Descriptive statistics will be provided. As appropriate, duration of response will be analyzed using the Kaplan-Meier method. Kaplan-Meier curves and estimates will be presented. Subjects without an objective response are excluded from the analyses of this endpoint. The median duration of response and other percentiles, as appropriate, and 80% CI will be presented. The percent of subjects with durable response at 6 and 12 months along with 80% CI will be presented.

Time to Response:

Descriptive statistics will be provided. As appropriate, time to response will be analyzed using the Kaplan-Meier method. Kaplan-Meier curves and estimates will be presented. The median time to response and other percentiles, as appropriate, and 80% CI will be presented.

Time to progression:

Time to progression will be analyzed using the Kaplan-Meier method. Kaplan-Meier curves and estimates will be presented. The median time to progression and other percentiles, as appropriate, and 80% CI will be presented. The percent of subjects who are progression-free at 6 and 12 months along with 80% CI will be presented.

Objective Response Rate:

Objective Response Rate will be analyzed using RANO Evaluable Analysis Set.

The number and proportion of patients with an objective response will be tabulated by AMG 596 dose received (MTD or other doses). An exact 80% confidence interval will be calculated using Clopper-Pearson method ([Clopper and Pearson, 1934](#). See [Appendix B](#) for code fragment) for the OR rate for all subjects in part 2 and those in part 1 treated at RP2D/MTD for each group.

Progression Free Survival:

Progression free survival (PFS) will be analyzed using the Kaplan-Meier method. Kaplan-Meier progression free survival curves and estimates will be presented. The median PFS and other percentiles, as appropriate, and 80% CI will be presented. The percentage of subjects alive and progression-free at 6 and 12 months along with 80% CI will be presented.

Response Criteria:

Response criteria will be analyzed using RANO Evaluable Analysis Set.

The number and percentage of subjects in each response category (CR, PR, SD and PD) will be tabulated by AMG 596 dose received (MTD or other doses).

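### The SAP efficacy set admits anyone ever dosed at the MTD but starts the PFS and TTP clock at the first dose of any level, so time before the MTD is credited to the MTD

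*SAP*

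**What the plan says.** SAP section 6 defines the Efficacy Analysis Set, which serves the secondary endpoints on efficacy, as follows: "All subjects that are enrolled and receive at least one administration of AMG 596 at the MTD will be included in the analysis". SAP 9.5 makes this set the default. SAP 9.5.1 moves only objective response rate (ORR) and response category to the RANO Evaluable set, so PFS and TTP stay in the default.

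SAP section 5 starts both clocks at the first dose, whatever its level. PFS is "The number of days from the date of first administration of AMG 596 to the date of radiological evidence of disease progression" or death. For TTP: "Time to progression is calculated as the number of days from the date of first administration of AMG 596" to the first radiographic progression. Landmark rates come from Kaplan-Meier curves with Greenwood intervals (SAP 9.5).

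Protocol 3.1 states: "Intra-subject dose escalation will be allowed to higher AMG 596 dose levels in subsequent treatment cycles", on the condition "once a higher dose has been deemed safe by the DLRT". Section 6.2.1.1 repeats the rule.

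SAP section 6 adds that "subjects will be analyzed according to the dose and treatment they received, not the dose and treatment to which they were assigned". It does not say how to classify a subject who received two dose levels. The ORR interval in SAP 9.5.1 is "for the OR rate for all subjects in part 2 and those in part 1 treated at RP2D/MTD for each group", and protocol 10.5.3 uses the same pool. Neither says whether escalators belong to it.

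**The concern.** Entry to the set depends on something that happens after time zero. Take two subjects who start in the cohort below the MTD. One stops after the first cycle and never enters. The other stays on treatment, is escalated, and enters with the lower-dose weeks counted as event-free time at the MTD. This is guarantee-time (immortal-time) selection. Neither document uses delayed entry, restarts the clock or classifies by starting dose.

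The 6- and 12-month PFS rates are secondary endpoints of a study without a control arm, so they are read as absolute rates and no comparator cancels the error. The listings in SAP 9.6.7 would show who escalated, but the PFS and TTP tables would not separate them.

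Three related gaps sit in the same text:

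- Time to response and duration of response have an attribution problem (which dose produced the response) rather than immortal time.
- The set names only the MTD, although SAP 3.1 foresees that none may be reached. Read literally, the set could then be empty.
- The set differs from protocol 10.5.3, which pools all Part 2 subjects with Part 1 subjects treated at the RP2D/MTD. SAP section 10 nevertheless reports no changes from the protocol.

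**Working it through.** **The plan's own figures.** For 21 subjects at the RP2D/MTD (6 + 15; protocol 10.2, SAP 3.2):

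- Chance of seeing an adverse event of 5% incidence: 1 − 0.95^21 = 66%.
- Chance of at least 4 responses at an ORR of 20%: 63%.
- Exact 80% interval for 4/21: 8.6% to 34.5%, stated as 9%-35%.

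All three reproduce. The documents state no expected PFS or TTP rate.

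**Inputs for the bias**

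- From the documents: n = 21 MTD starters in Group 1 and n = 31 in Group 2; sequential cohorts of 2-4.
- Assumed: exponential PFS; true 6-month (week 26) PFS of 20%; m = 4 or 8 candidates from the cohorts just below the MTD; a fraction f = 0.5 (or 1) of those still progression-free escalate at week w = 6, 12 or 18.

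**Formulas**

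- λ = −ln(0.20)/26 = 0.0619 per week, so S(6) = 0.690, S(12) = 0.476, S(18) = 0.328.
- Progression-free escalators: e = f·m·S(w).
- Reported rate at week T: [n·S(T) + e·S(T − w)]/(n + e).

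Example, Group 1, m = 4, f = 0.5, w = 6: e = 0.5 × 4 × 0.690 = 1.38 and S(20) = 0.290. Reported rate = (21 × 0.20 + 1.38 × 0.290)/22.38 = 20.6%.

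**Reported 6-month PFS when the true value is 20%**

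| Candidates, fraction | Group 1: week 6 / 12 / 18 | Group 2: week 6 / 12 / 18 |
|---|---|---|
| 4, half | 20.6 / 21.0 / 21.2% | 20.4 / 20.7 / 20.8% |
| 8, half | 21.0 / 21.8 / 22.4% | 20.7 / 21.3 / 21.7% |
| 8, all | 21.9 / 23.4 / 24.5% | 21.4 / 22.4 / 23.2% |

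**Other readings, Group 1, f = 0.5**

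- 12-month rate: 4.1% to 4.5% against a true 4.0%.
- Median: from 11.2 weeks to 11.6-12.6 weeks.
- True 6-month PFS of 10%: reads 10.4% to 11.5%.
- True 6-month PFS of 30%: reads 30.6% to 33.0%.

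**When the sign changes.** If a share q of escalators had already progressed, the bias is zero at q = 1 − S(w): 31%, 52% and 67% at weeks 6, 12 and 18. With q = 40% at week 6, Group 1 reads 19.5% to 19.7%.

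**Simulation** (Group 1, week 12, m = 8, f = 0.5; 8,000 runs, Monte Carlo SE 0.1 points): SAP set 21.6%; starting-dose set 19.8%; delayed entry at the first MTD dose 19.8%.

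**Heavier scenario.** Fix the number of progression-free escalators at six, crossing at 2.8 months (two 6-week cycles, an assumed length). Take true 6-month PFS of 6.7%, 15% or 25.3%; the outer values are rates that protocol 2.1 cites for recurrent glioblastoma. Simulation (4,000 runs) gives 10.5%, 19.6% and 30.2% under the SAP rule, and 6.7%, 14.9% and 25.2% with delayed entry. At 4.2 months the bias is 8.4 to 9.2 points. These cases need many candidates. At a true 15%, S(2.8 months) = 0.413 and S(4.2 months) = 0.265, so six progression-free escalators imply at least 6/0.413 = 14.5 or 6/0.265 = 22.6 lower-dose starters.

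**ORR illustration.** From 4/21 = 19.0%, one escalator who responded at a lower dose gives 5/22 = 22.7% (80% CI 11.5%-38.1%). One non-responding escalator gives 4/22 = 18.2% (8.2%-33.1%). The direction is unknown.

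**The case against.** **The arithmetic ignores how events are dated.** Apart from deaths, SAP 5 counts MRI-dated progression, and scheduled scans are 10 to 12 weeks apart (protocol 7.2.2). Without an early scan or a death, a week-6 escalator gains almost no guaranteed time, and week 18 selects no more than week 12. With two scheduled scans before month 6 and a 20% rate, survival past each scan is √0.20 = 0.447. Group 1 then reads 20.0% for week-6 escalators and 21.0% to 21.9% for week 12 or 18 (23.6% if all eight candidates still progression-free escalate). Group 2 reads 20.7% to 21.3% at week 12 or 18 (22.6% if all eight). This is fair as a lower variant, but it stays close to the range above. Early scans and deaths move it back.

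**Treatment past progression is allowed**, so an escalator may already have progressed. That stands as a limit on direction. However, the break-even shares are exactly what no selection for progression-free subjects would produce, so upward remains the expected sign.

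**The inputs are not in the documents.** This stands: the figures are scenarios, not estimates.

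**The SAP is simply behind the protocol.** It cites the protocol dated 05 July 2017. But Amendment 4, which lists intra-subject escalation among its revisions, is dated 11 March 2019, and SAP version 2.0 carries dates of 23 April and 20 May 2019. The lag explains the gap without excusing it.

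**The intent may be cohort-based.** The sample-size text counts 6 subjects from escalation, and SAP 9.1 plans summaries by dose. Neither settles where an escalator goes, and the dose-received sentence in SAP 6 points the other way.

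**Conclusion.** The concern holds. Followed as written, the SAP selects lower-dose starters on staying on treatment and credits their earlier time to the MTD. In the scenarios judged most plausible, the upward shift in 6-month PFS is about 0.6 to 2.4 points in Group 1 and 0.4 to 1.7 in Group 2. It reaches 4.5 and 3.2 points if all eight candidates who are still progression-free escalate. It is negligible at 12 months and larger only with many more escalators than sequential cohorts of 2-4 make likely. This is small beside the plan's precision, as the 80% interval of 9%-35% for 4/21 shows.

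Confidence is high in the mechanism and limited in the size, which rests on assumed escalator numbers, timing and exponential PFS. The bias is zero if nobody escalates, and the sign can reverse. No hypothesis test, futility rule, alpha or power figure is affected. It should be fixed because the rates are read as absolute values and the repair is cheap.

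**What to change.** - **SAP 6 and 9.5:** define the Efficacy Analysis Set, by arm and group, as all Part 2 subjects plus Part 1 subjects whose initial regimen (target dose if step-dosed) was the RP2D/MTD, or the Part 2 dose if no MTD is declared.
- **SAP 6, dose-received sentence:** state that for efficacy the dose received is classified by the initial regimen.
- **SAP 9.5.1:** apply the same rule to the ORR pool.
- **Escalators:** list them separately by starting dose, or include them in PFS and TTP only with delayed entry at their first MTD dose.
- **Part 2:** if the expansion dose is revised, report these subjects by starting dose, so that the pooled set does not hide a mixture.
- **Protocol 10.5.3 and SAP 10:** align the protocol clause and record the difference.

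The cost is wording in four SAP sections and one protocol clause. A few Part 1 escalators leave the main PFS and TTP tables unless delayed entry is used. No sample size, stopping rule, test or power figure changes.
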